### 8.3.2 MODIFIED SAFETY POPULATION

The modified safety population consists of any subject (or eye) who has signed the informed consent and has had the LAL or Control lens implantation attempted, which is defined as the point at which the lens makes contact with the eye. The Pre-COVID-19 study subjects will be excluded from this population. This population will be used for the safety summaries. The lens groups of this population will be based on the actual received lens. No imputation will be performed.

For subjects encountering intraoperative complications before study lens implantation, their intraoperative complications will be listed separately.

### 8.3.3 INTENT-TO-TREAT (ITT) POPULATION AND FULL ANALYSIS SET (FAS)

The intent-to-treat (ITT) population contains all of the randomized subjects regardless of having the study lens implantation attempted. Since randomized subjects may not have implantation attempted due to intraoperative complications during cataract extraction or for other reasons such as delays due to the COVID-19 pandemic, the ITT population will not be used for the primary effectiveness analyses. Instead, the Full Analysis Set (FAS) which is defined as the ITT subjects with study lens implantation attempted (regardless of successful implantation) after cataract extraction will be used for the primary effectiveness analyses. The Pre-COVID-19 study subjects will be excluded from this population. The primary analyses of the primary effectiveness endpoints and the monocular outcomes of the secondary effectiveness endpoints will be based on the primary eyes of the FAS; the primary analyses of the binocular outcomes of the secondary effectiveness endpoints will be based on the subjects in the FAS. The analysis group will be based on the randomized group (LAL versus Control), not based on the actual lens received.

For the subjects that do not have the available data of the primary or secondary effectiveness endpoints or have lens exchange or explants before Postop Month-6, the imputation described in Section 8.5.1 will be used for the primary analysis of the primary and secondary effectiveness endpoints. Different imputations will be included in the sensitivity analyses described in Section 8.5.2 below.

### 8.3.4 PER-PROTOCOL (PP) POPULATION

The per-protocol population is a subset of the FAS and is comprised of the FAS subjects that do not have any major protocol deviations. Major protocol deviations will include those deviations that may impact subject safety, affect the integrity of study data and/or affect subject willingness to participate in the study, such as implantation, adjustment and lock-in procedures that are not performed as specified in the protocol and/or Operator's manual. The PP population will be used for supportive effectiveness analyses.

## 8.4 BASELINE CHARACTERISTICS

Demographics (such as age, gender, and race) and baseline characteristics will be summarized for the safety population and FAS subjects by the lens group (LAL versus Control lens). For the monocular measurements, the summary will be prepared for the primary eyes and the fellow eyes separately. The data of the fellow eyes that do not have the LAL or the control lens implanted will be excluded from the fellow-eye summaries and, if needed, may be listed separately.

The analyses will also be stratified by the study site in order to assess the similarity of these baseline characteristics among the study sites.

## 8.5 EFFECTIVENESS ANALYSES

The primary analyses for the primary effectiveness endpoints will be based on the FAS population described in Section 8.3.3. For each type of visual acuity for eyes with study lens exchange or explants before Postop Month-6, the worst observed Month-6 visual acuity of the corresponding lens group will be used to impute the Month-6 visual acuity whether or not the Month-6 data is available.

### 8.5.1 PRIMARY ANALYSES FOR THE EFFECTIVENESS ENDPOINTS

For the primary analyses of the primary and secondary effectiveness endpoints, the missing Postop Month-6 visual acuity will be imputed by the worst observed Month-6 visual acuity of the corresponding lens group.

#### **First Co-Primary Effectiveness Endpoint**

From the depth of focus test, the mean logMAR visual acuity of the primary eyes will be calculated and plotted against the corresponding lens diopter of the defocusing lens (defocus curve) at Postop Month 6 for the LAL and Control groups, separately. In case of missing visual acuity values from the depth of focus test, the worst observed visual acuity value of the corresponding defocusing lens diopter at Postop Month 6 of the same lens group will be used to impute the missing visual acuity values at Postop Month 6. A horizontal line at a Y-axis value of logMAR 0.20 will be included in the defocus curves. The lens diopter values corresponding to the intercepted point of the 0.20 logMAR horizontal line and the defocus curve for the negative diopter value will be estimated. The DOF at Postop Month 6 is the absolute difference between the negative lens diopter values corresponding to the 0.20 logMAR visual acuity and 0 diopter. The DOF at Postop Month 6 will be calculated for the two lens groups separately and numerically compared to the target difference value of 0.5 D. No formal statistical comparison will be performed.

#### **Second Co-Primary Effectiveness Endpoint**

The analysis will be based on the primary eyes of the FAS. The mean, standard deviation (SD), 95% confidence interval of the mean based on one-sample t-distribution, median, minimum, and maximum will be derived for logMAR monocular photopic DCIVA at Postop Month 6. [REDACTED]

### **Third Co-Primary Effectiveness Endpoint**

The count and percent of the primary eyes of the LAL subjects in the FAS that have a monocular photopic DCIVA of 0.20 logMAR or better at Postop Month 6 will be calculated.

### **Fourth Co-Primary Effectiveness Endpoint**

The analysis will be based on the FAS primary eyes. The mean, standard deviation (SD), 95% confidence interval of the mean based on one-sample t-distribution, median, minimum, and maximum will be derived for logMAR monocular photopic BCDVA by the lens group.

### **First Secondary Effectiveness Endpoint**

The analysis will be based on the primary eyes of the FAS. The mean, standard deviation (SD), 95% confidence interval of the mean based on one-sample t-distribution, median, minimum, and maximum will be derived for logMAR monocular photopic DCNVA at Postop Month 6.

### **Second Secondary Effectiveness Endpoint**

The count and percent of the primary eyes that have a monocular photopic DCNVA of 0.20 logMAR or better at Postop Month 6 will be calculated for the LAL subjects in the FAS.

**Third Secondary Effectiveness Endpoint**

[figure not shown]

**Fourth Secondary Effectiveness Endpoint**

**Fifth Secondary Effectiveness Endpoint**

The analysis will be based on the primary eyes of the FAS. The mean, standard deviation (SD), 95% confidence interval of the mean based on one-sample t-distribution, median, minimum, and maximum will be derived for logMAR monocular photopic UCDVA using a +0.25 D lens at Postop Month 6.

### 8.5.2 SECONDARY/SENSITIVITY ANALYSES FOR THE PRIMARY EFFECTIVENESS ENDPOINTS

The analyses described in Section 8.5.1 will be performed based on the PP population. Additionally, for the primary and secondary effectiveness endpoints, the analyses described in Section 8.5.1 will be performed based on the fellow eyes with lens implantation.

If there are FAS primary eyes with missing primary or secondary effectiveness endpoints but without lens reposition or explants before Postop Month 6, the analyses described in Section 8.5.1 will be performed using the following imputations for missing distance corrected visual acuity or uncorrected visual acuity (based on logMAR value) for eyes/subjects without secondary surgical interventions (SSI):

- Mean of observed logMAR value for the corresponding effectiveness endpoint in the corresponding lens group.
- Mean of observed logMAR value for the corresponding effectiveness endpoint in the other lens group.
- Worst observed logMAR value of the corresponding effectiveness endpoint in the other lens group. (note: use of the worst observed logMAR value in the corresponding lens group has been described in Section 8.5.1)
- Best observed logMAR value for the corresponding effectiveness endpoint in the corresponding lens group.
- Best observed logMAR value for the corresponding effectiveness endpoint in the other lens group.

Additionally, a tipping point analysis will be performed with imputations for eyes/subjects with missing values and without SSI as follows:

#### **Continuous Outcomes: 2nd and 4th primary effectiveness endpoints and 1st and 5th secondary effectiveness endpoints**

For each endpoint, each missing value of the LAL group will be imputed by the observed mean logMAR value of the LAL group added by an increment of 0.01 (i.e. 0.01 logMAR worse) sequentially; the missing value of the Control group will be imputed by the observed mean logMAR value of the Control group subtracted by an increment of 0.01 (i.e. 0.01 logMAR better) sequentially. Except for the 5th secondary effectiveness endpoints, the one-sided p-value of the two-sample t-test will be calculated based on the combinations of imputations until the p-value becomes  $> 0.025$  (i.e. insignificant) or until the imputed value is the observed worst logMAR of the two lens group for the LAL group and the observed best logMAR value of the two lens group for the Control group, which comes first. The F-test of the ANCOVA will be performed for the 5th secondary effectiveness endpoint.

**Dichotomous Outcomes: 3rd primary effectiveness endpoint and 2nd, 3rd, and 4th secondary effectiveness endpoint**

For each endpoint, the analysis will assume all missing responses for the LAL group are non-responders, then one is responder and all other are non-responders, and gradually proceed to all missing responses for the LAL group are responders; similarly, the assumptions will be made for the missing response for the Control group. For the third secondary effectiveness endpoint, the p-value based on an approximate z-test will be calculated for each combination. For the third primary effectiveness endpoint and the second and fourth secondary effectiveness endpoint, the 95% confidence interval of the proportion will be calculated for each of the LAL-group assumption and these confidence intervals will be plotted.

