## 1.6 OUTCOME PARAMETERS

### Effectiveness Parameters:

#### *Primary Endpoints*

- Monocular Depth of Focus (DOF) measured at the logMAR 0.20 level at Postop Month 6

At Postop Month 6, the LAL group (primary eyes) demonstrates at least 0.5 D greater monocular photopic negative lens induced distance-corrected depth of focus compared to the Control group (primary eyes) at 0.20 logMAR visual acuity threshold.

- Monocular photopic Distance Corrected Intermediate Visual Acuity (DCIVA) at 67 cm at Postop Month 6

At Postop Month 6, the LAL group (primary eyes) demonstrates statistical superiority over the Control group (primary eyes) on mean monocular photopic DCIVA at 67 cm. [one-sided test using level of significance of 0.025]

- Outcome of Monocular photopic DCIVA at 67 cm better than or equal to 0.20 logMAR for the LAL group at Postop Month 6

At Postop Month 6, the proportion of the LAL primary eyes reaching this outcome is at least 50%. In other words, the median of photopic monocular DCIVA at 67 cm for the LAL group (primary eyes) is at least 0.20 logMAR.

- Monocular photopic Best Corrected Distance Visual Acuity (BCDVA) at Postop Month 6

At Postop Month 6, the LAL group (primary eye) is statistically non-inferior to the Control group (primary eyes) on mean of monocular photopic BCDVA using a non-inferiority margin of 0.10 logMAR.

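### For continuous endpoints, the own-mean fill and tipping-point analysis in Section 8.5.2 treat one constant per arm as observed data, which understates the standard error and places the tipping point modestly too far out

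*Combined protocol and SAP*

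**What the plan says.** All of this is in Section 8.5.2, whose text on these points is readable.

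- **Simple fills.** For primary eyes in the Full Analysis Set with missing endpoints and no secondary surgical intervention, "the analyses described in Section 8.5.1 will be performed using the following imputations for missing distance corrected visual acuity or uncorrected visual acuity". The first fill listed is "Mean of observed logMAR value for the corresponding effectiveness endpoint in the corresponding lens group". The others are the other group's mean, the other group's worst value, and the best value of either group.
- **Tipping point, continuous endpoints** (second and fourth co-primary, first and fifth secondary). In the LAL arm "each missing value of the LAL group will be imputed by the observed mean logMAR value of the LAL group", made worse in 0.01 logMAR steps. In the Control arm "the missing value of the Control group will be imputed by the observed mean logMAR value of the Control group subtracted by an increment of" the same size. Then "the one-sided p-value of the two-sample t-test will be calculated based on the combinations of imputations until the p-value becomes" larger than 0.025, or until LAL has reached the worst and Control the best observed value. The fifth secondary endpoint uses an ANCOVA F-test instead.
- **Variance.** The readable text has no multiple imputation, no between-imputation variance and no correction of the sample size, SE or degrees of freedom.

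The between-group test in Section 8.5.1 is redacted. The synopsis gives the level for intermediate acuity superiority as "one-sided test using level of significance of 0.025".

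**The concern.** A constant placed at the arm mean adds nothing to the sum of squares, yet the t-test counts each filled eye as a measurement. The apparent sample size rises from the number observed to the number randomised and implanted, and the pooled SD falls. Both changes make the SE too small.

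These analyses exist to show how far the missing-data assumptions can be pushed before the superiority and non-inferiority results are lost. If the search starts from a p-value that is already too small, the reported tipping point is too far out and the result looks sturdier than it is. The distortion matters most when the primary result lies close to the 0.025 boundary, which is where a reader relies on a tipping-point analysis.

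**Working it through.** **Inputs.** N = 112 per arm (Section 8.1.2); 1:1 allocation; one-sided 0.025; fills and test as in Section 8.5.2. The SD and the assumed effects are redacted, so results are in SD units. The missing rate is an assumption, shown over a range.

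**The plan's own figure.** 100 / (1 − 0.10) = 111.1, rounded up to 112. This matches Section 8.1.2; 2 × 112 = 224, against the plan's upper limit of 230.

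**Own-mean fill (zero shift).** Let m be the number of eyes observed per arm, with the same m in both arms.

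- Correct variance of an arm mean: 1/m.
- Variance reported after the fill: (m − 1) / [(N − 1)N].
- SE ratio: √{m(m − 1) / [N(N − 1)]}.
- The t-test on filled data rejects when the observed-data t exceeds 1.971 × ratio (1.971 is the 222 df critical value). The true error is that tail of a t distribution with 2m − 2 df.

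| Missing | m | SE ratio | True one-sided error |
|---|---|---|---|
| 2% | 110 | 0.98 | 2.7% |
| 5% | 106 | 0.95 | 3.2% |
| 10% | 101 | 0.90 | 3.9% |
| 15% | 95 | 0.85 | 4.8% |

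For example, at 10%: √(101 × 100 / 12,432) = 0.901; 1.971 × 0.901 = 1.776; the tail on 200 df is 0.0386. Simulations with data missing completely at random gave 3.1 to 3.3%, 3.8% and 4.7% at 5%, 10% and 15%. The t-test on observed eyes only stayed at 2.4 to 2.6%.

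**Tipping point (shift d in SD units, equal in both arms).** Let π = (N − m)/N.

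- Plan's variance per arm: [(m − 1) + m(N − m)/N × d²] / [(N − 1)N].
- Delta-adjusted multiple imputation, large-sample: 1/m + π(1 − π)d²/N.

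At 10% missing and d = 1, the plan's variance is (100 + 9.92)/12,432 = 0.00884 and the reference is 0.00990 + 0.00079 = 0.01069. The SE ratio is √(0.00884/0.01069) = 0.91. It is 0.90 at d = 0 and 0.93 at d = 2.

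The tipping shift solves (effect − 2πd) / √(2 × variance) = critical t, with 222 df for the plan and 200 df for the reference. At 10% missing:

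| Assumed effect (SD) | Plan tips at | Multiple imputation tips at | Too far out by | SE fixed at SD/√m tips at |
|---|---|---|---|---|
| 0.30 | 0.25 | 0.11 | 0.14 | 0.11 |
| 0.42 | 0.82 | 0.70 | 0.12 | 0.73 |
| 0.48 | 1.10 | 0.98 | 0.12 | 1.03 |
| 0.60 | 1.63 | 1.52 | 0.11 | 1.64 |
| 1.00 | 3.27 | 3.19 | 0.08 | 3.68 |

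Effects of 0.42 and 0.48 SD are those that 90 per arm (Section 8.1.1) detects with 80% and 90% power: (1.960 + 0.842) × √(2/90) = 0.42 and (1.960 + 1.282) × √(2/90) = 0.48.

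**Null rejection under shift.** At 10% missing, d = 0.15 in both arms moves the difference against LAL by 2 × (11/112) × 0.15 = 0.029 SD. The rejection threshold is 1.971 × 0.127 = 0.250 SD. The true SE of the difference is √(2/101) = 0.141. So z = (0.250 + 0.029)/0.141 = 1.99, a rejection rate of about 2.3%.

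**In logMAR.** If the SD is assumed to be 0.10 to 0.20 logMAR, the displacement is 0.08 × 0.10 = 0.008 to 0.14 × 0.20 = 0.028 logMAR, or about one to three of the plan's steps.

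**The case against.** The strongest reply is that these are supportive analyses and the effect is small. Several parts of it stand.

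- **The error rates belong to zero shift.** A reader might infer that the tipping-point analysis runs at 3.9% or 4.8% type I error. The documents do not support that: the plan moves LAL worse and Control better, and at 10% missing null rejection is already below 2.5% at a shift of 0.15 SD. For that analysis the displacement of the tipping point is the right measure.
- **The trial's decision does not rest here.** A reader might also infer inflated error for the co-primary claims. Those claims use the primary analysis in Section 8.5.1, which fills with the worst value of the same arm; that is a separate question. Section 8.5.2 adds worst and best fills and a per-protocol analysis.
- **The SD is not always shrunk.** As the shift grows, the constants widen the pooled SD. Against SD/√m the understatement vanishes at a shift of about 1.5 SD, and for effects of 0.60 SD or more the plan no longer tips late (last column of the table). Against delta-adjusted multiple imputation it persists at every shift checked.
- **The 10% is borrowed.** It is the drop-out rate behind the safety sample size, not a forecast of missing Month 6 acuity. The fills cover only eyes without secondary surgical intervention.
- **One test is unseen.** That the own-mean rerun uses a t-test is inferred from the tipping-point text.

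None of this makes the SE right. The tipping-point t-test is explicit, no readable text corrects its variance, and a tipping-point analysis is read on its own terms.

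**Conclusion.** Wrong as written, with a modest effect. Own-mean fill gives an SE about 0.95, 0.90 and 0.85 of the correct one at 5%, 10% and 15% missing. The one-sided error is then about 3.1 to 3.2%, 3.8 to 3.9% and 4.7 to 4.8% in place of 2.5%, provided the redacted Section 8.5.1 comparison is a t-test. The continuous tipping-point analysis tips about 0.08 to 0.14 SD too late at 10% missing, relative to delta-adjusted multiple imputation.

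At 2% missing the effect on the p-value is nearly nil (2.7% against 2.5%). With an effect near 1 SD the tipping shift moves only from 3.19 to 3.27 SD, so the conclusion would be unlikely to change. It could matter for a result near the boundary.

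The figures assume 112 per arm, equal missingness and equal shifts in both arms, data missing completely at random for the error rates, and 10% as an assumed rate for missing Month 6 acuity. The mechanism carries over to the ANCOVA F-test for the fifth secondary endpoint, which was not separately quantified. The dichotomous tipping-point analysis counts through responder combinations, uses no mean fill, and is unaffected. The worst-value primary analysis is outside this point.

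**What to change.** In Section 8.5.2, for the continuous endpoints only:

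1. Impute missing Month 6 values within arm by multiple imputation, using Month 3 acuity as a predictor where it is collected. State the imputation model, the number of imputations and the seed.
2. Add the same 0.01 logMAR steps to the imputed values as per-arm delta adjustments: worse for LAL, better for Control.
3. Run the planned t-test (or the ANCOVA for the fifth secondary endpoint) on each completed dataset, combine by Rubin's rules, and report where the combined one-sided p-value passes 0.025.
4. Replace own-mean fill with the delta = 0 case.

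The cost is SAP wording, somewhat more programming, and slightly less favourable sensitivity p-values. Study conduct, endpoints, sample size and the primary analysis stay as they are.

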### 8.5.3 COVARIATES AND SUBGROUP ANALYSES

The purpose of performing the covariates and subgroup analyses are to evaluate the possible effects of these covariates on the primary effectiveness endpoints. The intention of these analyses is not for claiming treatment effect on any subgroups. The following covariates will be evaluated based on the imputation for the missing data used for the primary analyses:

- Age group (based on observed quartiles)
- Gender (male and female)
- Race (White and non-White)
- Ethnicity (Hispanic-Latino and not Hispanic-Latino)
- Study site
- MRSE at Postop Week 3 ( $\leq -3.00$  D,  $> -3.00$  D to  $-2.00$  D,  $> -2.00$  D to  $-1.00$  D,  $> -1.00$  D to  $< 1.00$  D,  $\geq 1.00$  to  $< 2.00$  D,  $\geq 2.00$  to  $< 3.00$  D, and  $\geq 3.00$  D)
- MRCYL at Postop Week 3 ( $< 0.50$  D,  $\geq 0.50$  D to  $< 1.00$  D,  $\geq 1.00$  to  $< 2.00$  D,  $\geq 2.00$  to  $< 3.00$  D, and  $\geq 3.00$  D)
- DEQ at Postop Week 3 (0.00 D to  $< 1.00$  D,  $\geq 1.00$  to  $< 2.00$  D,  $\geq 2.00$  to  $< 3.00$  D, and  $\geq 3.00$  D)

For the first co-primary effectiveness endpoint, the difference in monocular DOF at Postop Month 6 between the two lens groups will be derived for each level of each covariate. Additionally, DOF and the difference in DOF between the two lens groups will be stratified by the photopic pupil size ( $< 3.0$  mm,  $\geq 3.0$  to  $\leq 4.0$  mm, and  $> 4.0$  mm) measured at Postop Month 6. Meanwhile, the analysis will be performed by the axial length measured preoperatively ( $< 21.0$  mm, 21.0 mm to  $\leq 26.0$  mm, and  $> 26.0$  mm).

For the continuous effectiveness endpoints (the second and fourth co-primary effectiveness endpoints and the first and fifth secondary effectiveness endpoints), the mean, SD, 95% confidence interval of the mean, median, maximum, and minimum will be calculated by lens group for each level of each covariate. For each covariate, the mean differences among different levels of the covariate will be compared based on two-way analysis of variance (ANOVA) with lens group, covariate, and interaction of lens group and covariate as the

factors. A p-value of 0.15 will be used for evaluating the possible covariate and interaction effects.

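### The only between-group test visible for DCIVA, BCDVA and DCNVA is an unadjusted t-test; a prespecified ANCOVA with age and preoperative BCDVA could gain some precision at almost no cost

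*Combined protocol and SAP*

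**What the plan says.** The endpoint definitions in sections 1.6 and 5.1 set a superiority test for mean DCIVA ("one-sided test using level of significance of 0.025") and a non-inferiority comparison for mean BCDVA ("using a non-inferiority margin of 0.10 logMAR").

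In section 8.5.1 the paragraphs on these two endpoints show only summary statistics: for DCIVA they "will be derived for logMAR monocular photopic DCIVA at Postop Month 6", and for BCDVA they "will be derived for logMAR monocular photopic BCDVA by the lens group". The DCIVA paragraph then runs into a redaction. Neither paragraph shows a between-group test.

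Section 8.5.2 introduces a missing-data exercise: "Additionally, a tipping point analysis will be performed with imputations for eyes/subjects with missing values and without SSI as follows". Under it, for the continuous endpoints other than the fifth secondary, "the one-sided p-value of the two-sample t-test will be calculated", and the stepping ends once p exceeds 0.025. The fifth secondary is treated differently: "The F-test of the ANCOVA will be performed for the 5"th secondary endpoint. The covariate of that ANCOVA is not visible.

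Section 8.5.3 lists age group, gender, race, ethnicity, study site, and three refractive measures at Postop Week 3 (MRSE, MRCYL, DEQ). The purpose is "to evaluate the possible effects of these covariates on the primary effectiveness endpoints". For the continuous endpoints each covariate enters a two-way ANOVA with lens group and their interaction, one covariate at a time, judged at p = 0.15.

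**The concern.** An outcome compared between randomised arms can be estimated more precisely if the model includes baseline variables that predict it. The visible test uses none. Yet the SAP already plans an ANCOVA for one secondary endpoint and looks at age and site one at a time. Tables 1 and 2 schedule preoperative distance-corrected acuity in both arms. Section 7.2 places randomisation immediately before surgery on the primary eye, so that measurement precedes it.

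At stake is the width of the interval for DCIVA superiority, for BCDVA non-inferiority, and for DCNVA. The type I error rate is not in question.

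**Working it through.** **Which test is the primary one?** The t-test is readable only in the tipping-point rule. Two features suggest that this rule mirrors section 8.5.1. It stops at 0.025, the level set for DCIVA. It also changes method by endpoint: t-test, ANCOVA for the fifth secondary, z-test for the third secondary, and confidence intervals for the single-arm proportions. An unadjusted primary test is therefore a sound inference, but it cannot be read directly.

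**The plan's own figures.** Section 8.1.2: 100 / (1 − 0.10) = 111.1, rounded up to 112 per arm, which matches the plan; 2 × 112 = 224. The 180 (90 × 2) in section 8.1.1 cannot be reproduced, because the effect sizes, SDs and power are not visible.

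**Formula.** Let R² be the within-arm outcome variance explained by all covariates in the model, p the number of covariate terms, and N the total analysed. Relative to the t-test,

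variance ratio ≈ (1 − R²) × [1 + p / (N − p − 3)], and SE ratio = its square root.

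The bracket is the expected price of chance imbalance in the covariates when randomisation does not balance them. Section 7.2 states blocks of 4 and no stratification factor.

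**Inputs.** N = 224, since the FAS imputes missing values. R² is not in the documents; 0.02 to 0.15 is assumed.

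- Age and preoperative BCDVA: p = 2, bracket = 1 + 2/219 = 1.0091.
- Site (at most 11 sites, so 10 terms) plus age: p = 11, bracket = 1 + 11/210 = 1.0524.

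| Assumed R² | p = 2: variance ratio | SE change | p = 11: variance ratio | SE change |
|---|---|---|---|---|
| 0.02 | 0.98 × 1.0091 = 0.989 | −0.6% | 0.98 × 1.0524 = 1.031 | +1.6% |
| 0.05 | 0.95 × 1.0091 = 0.959 | −2.1% | 0.95 × 1.0524 = 1.000 | 0.0% |
| 0.10 | 0.90 × 1.0091 = 0.908 | −4.7% | 0.90 × 1.0524 = 0.947 | −2.7% |
| 0.15 | 0.85 × 1.0091 = 0.858 | −7.4% | 0.85 × 1.0524 = 0.895 | −5.4% |

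Break-even R² is 1 − 1/1.0091 = 0.009 for two covariates and 1 − 1/1.0524 = 0.050 for site plus age. Dividing 112 by the p = 2 variance ratios gives an equivalent of about 1, 5, 11 or 19 extra subjects per arm.

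**Power already available.** For an effect with 80% (90%) power at 90 per arm, one-sided 0.025, the unadjusted test has 87.8% (95.1%) power at 112 per arm. For BCDVA with a true difference of 0 and 90 per arm, unadjusted power is 99.4%, 96.1% and 91.8% at assumed SDs of 0.15, 0.18 and 0.20 logMAR.

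**The case against.** Most of the case on the other side stands.

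- **The t-test is valid.** A reader might infer that the plan uses a wrong test. It does not: randomisation is 1:1 and no stratification factor is stated, so the visible text shows no mismatch between design and analysis.
- **The primary test is not readable.** A reader might state as fact that section 8.5.1 uses an unadjusted t-test. The quoted test belongs to a missing-data sensitivity analysis, so the claim must stay at apparently.
- **The plan does not name preoperative measures as likely predictors of these endpoints.** Section 8.5.3 speaks only of possible effects. Its refractive covariates are taken after randomisation and implantation. Preoperative axial length appears there only for depth of focus, which has no formal test. Preoperative BCDVA is collected but is not on the list.
- **Covariates are already examined.** The two-way ANOVAs will show the influence of age and site. They do not enter the main comparison.
- **Adding site is not free.** Ten site terms plus age lose precision below R² of about 0.05. If blocks were formed within site, which is not stated, simulated inflation is only about 1.006, but then little site imbalance is left to correct.
- **Predictors may be weak.** DCIVA and DCNVA appear to be scheduled only from Month 3. Preoperative BCDVA partly reflects the cataract that surgery removes, and eligible eyes must be projected to reach 20/20.
- **Little power is at stake**, because safety sizing already exceeds the effectiveness requirement.

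These points defeat a claim of error and a claim of material lost power. They do not touch a two-covariate adjustment, whose expected cost is under 1% of variance.

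**Conclusion.** The point holds as an optional efficiency improvement. The visible test for DCIVA, BCDVA and DCNVA is unadjusted and the primary test is apparently the same. Adjusting for age and preoperative BCDVA lowers the expected SE once the two together explain about 1% of outcome variance. The size of the gain cannot be derived from the documents; it is about 0.6% to 7.4% of the SE over the assumed R² range. That range rests on N of about 224 and on randomisation that does not balance the covariates. The lower end is plausible for DCIVA and DCNVA. Nothing here threatens the trial's conclusions.

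**What to change.** In section 8.5.1, prespecify the main comparison for DCIVA, BCDVA and DCNVA as an ANCOVA with lens group, age as a continuous variable, and preoperative BCDVA of the primary eye. Test the adjusted difference one-sided at 0.025, against the 0.10 logMAR margin for BCDVA. Use the same model in the tipping-point analysis, so that it probes the primary conclusion. Keep the two-sample t-test as supportive.

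Do not adjust for Postop Week 3 refraction. Put site in the main model only if randomisation was blocked within site, and say in section 7.2 whether it was; otherwise keep a site-adjusted model as supportive.

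The cost is SAP wording and a slightly more complex model, fixed before unmasked data are seen. No new data, visits or subjects are needed. If the redacted part of section 8.5.1 already specifies such a model, only the tipping-point rule needs aligning.
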